1.1 Background

Colorectal Cancer Disparities. In the US, CRC is the third most commonly diagnosed cancer and the second most deadly cancer. The CRC incidence (45 vs 39 per 100,000) and mortality (16 vs 14 per 100,000) in the Virginia Commonwealth University (VCU) Massey Cancer Center (MCC) Catchment Area are slightly higher than the US. Compared to whites in the catchment, AA/Blacks experience higher incidence of colorectal (42 vs. 37 per 100,000). Notably, 26 of the 65 counties in the MCC catchment area are part of Southside VA and it is recognized as a national "hot spot" for CRC where Petersburg City, our

pilot site is located. Moreover, Petersburg has a large AA/Black population, many of whom experience poverty or lower socioeconomic status.

AA/Black Men's Barriers to CRC Screening. Factors associated with CRC screening include physician recommendation, social support, medical mistrust, perceived discrimination, and avoidance. While many of these factors (e.g., physician recommendation) are relevant for AA/Black men, several factors such as medical mistrust and discrimination may exacerbate screening behaviors. For AA/Black men, avoidance, fear, and perceived discrimination contribute to low screening and play a critical role in their healthcare utilization, health behaviors, and mortality. Though acknowledged, the extent to which cultural attitudes related to avoidance and medical mistrust dissuade participation in preventive CRC screening is unclear. Mistrust of the healthcare system and experiences of racial discrimination are associated with lower health services utilization among AA/Black patients and is a widely cited attitudinal barrier to CRC screening. AA/Black men expressed explicit fears of medical experimentation and uneasiness about the invasiveness of colorectal cancer screening procedures (e.g., colonoscopy). Therefore, CRC interventions tailored for AA/Black men must address concerns of medical mistrust and discrimination. Studies have indicated that social support is correlated with having a colonoscopy. Kinney et al., found that the association between social connection and CRC screening was stronger for AA/Blacks than for whites. Interventions promoting CRC screening exist but few addressed the unique needs of AA/Black men.

2 - Rationale/Significance/Problem Statement

2.1 Rationale

This project will address CRC screening among AA/Black men within the MCC catchment area. This is significant because AA/Black men remain a dramatically underserved group that has not equally benefited from existing colorectal cancer (CRC) education or screening interventions. Moreover, within the MCC catchment area is one of three enduring national CRC hotspots.

2.2 Significance

Clinically, this is significant because AA/Black men remain a dramatically underserved group that has not equally benefited from existing colorectal cancer (CRC) education or screening interventions. Moreover, as MCC is a member of the National Outreach Network (NON), an efficacious mHealth Screen to Save (S2S) for AA/Black men would have population-level impact through scalability to all NON CHEs. The proposed study will fill a gap in translational research by conducting qualitative and survey research pilot work to inform the tailoring of an existing screening intervention, Screen 2 Save, to develop and test an enhanced mHealth S2S intervention culturally tailored for African American (AA)/Black men. The testing of the intervention will be conducted as part 2 and will not begin until an amendment is approved by the IRB.

3.1 Purpose

While many factors associated with CRC screening (e.g., clinician recommendation) in the general population may also be relevant for AA/Black men, certain factors may be exacerbated and/or unique to

them. For example, medical mistrust and expectations of poor care due to perceived discrimination and racism, attitudes about the value of preventive care and concerns about test invasiveness and fear can dissuade screening, particularly for colonoscopies, as screening can be considered intrusive and embarrassing. Supportive social networks (e.g., friends, community leaders) may endorse and encourage the prioritization of personal preventive health behaviors while simultaneously attenuating fear and embarrassment that impede screening uptake. The lack of detailed empirical data about relationships among these factors and how they influence CRC in AA/Black men has hampered progress in the field. This study will collect in-depth information about AA/Black men's CRC screening practices and collect data necessary for the adaptation and development of a mHealth Screen 2 Save intervention to increase CRC screening among AA/Black men in Petersburg and Richmond, VA.

3.2 Hypothesis

H1.1. Lack of social support, higher medical mistrust, and perceived discrimination will be negatively associated with self-reported guideline concordant screening behaviors.

H2.2. Higher engagement in preventive care behaviors and greater perceived risk will be associated with higher completion of CRC screening. Subaim1a. Examine potential interactions between perceived discrimination, medical mistrust and engagement in preventive care behaviors.

H1.3. Increased perceptions of discrimination and greater medical mistrust will attenuate the relationship between preventive care and guideline concordant screening.

3.3 Objectives

Aim 1. Determine factors associated with self-reported CRC screening behaviors among (n=175) AA/Black men in Petersburg, VA.

Aim 2. Develop tailored S2S content for AA/Black men to be delivered using a combination of short video and text-based information optimized for delivery via smartphones.

Aim 3. Test intervention on a sample of n=30 AA/Black men who are due for CRC screening. The primary aim is completed CRC screening (any type) at 3months. Secondary aims are to collect process date to assess satisfaction and feasibility.

4 - Study Participants

4.1 Study Population

AA/Black men remain a dramatically underserved group that has not equally benefited from existing colorectal cancer (CRC) education or screening interventions. African American/Black men experience 20% higher incidence, 45% higher mortality, have the shortest CRC survival rates of all racial/ethnic groups. CRC screening participation rates among Black men are 10%-30% lower than other groups. The focus of this project is to: PART 1: identify risk factors associated with screening behaviors in Black men

and, PART 2 (not submitted yet): develop a scalable mobile Health (mHealth) tailored S2S intervention to address those factors that keep Black men from completing CRC screening. Therefore, we focus on recruiting Black men only.

4.2 Number of Participants

We require 8-10 men for the Community Advisory Board and we require n=175 Black or African American for survey in PART1. The intervention component will require n=30 men

Total study n=225

The survey component was powered on the interaction term "discrimination*preventive care engagement", both continuous, using a simulation study of 1000 runs of a logistic regression model, with the binary screening behavior response (1 = screened, 0 = not screened). A sample size of 175 subjects generates 80% power to detect a "small to moderate" effect size of 0.38 (corresponding odds ratio = 2.01, using R package "effect size") for the interaction term (continuous*continuous), at 5% level of significance, using a one-sided Z-test. To account for individuals who start but do not complete the survey we have added a buffer of 20% which gives a sample size of n=210 for the survey. The sample size has been chosen for the intervention to support an initial examination of intervention effectiveness using a one-arm design. This is a typical size that will generate pilot data on the feasibility of our approach.

4.3 Selection Criteria

Survey Eligibility Criteria: Men aged 45-75 who reside in Petersburg and identify as AA/Black and have no personal history of cancer.

CAB/Focus Group Criteria: adult men, identify as Black or African American, work or live in a Petersburg VA or surrounding counties and are interested in participating. They do not need to meet requirements for population based CRC screening.

Intervention Aim 3: adult men, identify as Black or African American, work or live in a Petersburg VA, aged 45-74, eligible for CRC screen at study enrollment

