[figure not shown]

CLINICAL STUDY PROTOCOL

MCC-21-18632

SUCCEED: Engaging Black Men in CRC Screening

NCT05980182

9/08/2021

SUCCEED: Engaging Black Men in CRC Screening

Protocol Number

HM20023619

Principal Investigators

[name] (VCU)

[name] (VSU)

Protocol Version

8 September 2021

VCU Study Personnel

Principal Investigator	[name] Email: [contact]
Co-Investigator	
Research Assistant	
Student/RA	

Synopsis

Purpose

To determine the unmet needs, attitudes, barriers and facilitators of AA/Black men use of colorectal cancer screening and describe how community leaders such as barbers may act as Community Champions to educate and facilitate screening participation.

Objectives

Aim 1. Determine factors associated with self-reported CRC screening behaviors among (n=175) AA/Black men in Petersburg, VA.

Aim 2. Develop tailored S2S content for AA/Black men to be delivered using a combination of short video and text-based information optimized for delivery via QR codes for smartphones.

Aim 3. Test intervention on a sample of n=30 AA/Black men who are due for CRC screening. The primary aim is: completed CRC screening (any type) at 3months. Secondary aims are:

to collect process data to assess satisfaction and feasibility.

H1. Preliminary effectiveness of the intervention will be shown with >60% of men enrolled obtaining a CRC screen (any modality) by 12 weeks

H2. At Week 2 >80% of men enrolled will endorse an intention to be screened

H3. We will be able to recruit a sample of n=30 men into the intervention and maintain a retention rate (completion of baseline, 2 and 12 week surveys) >75%

Study Population

Survey Eligibility Criteria: Men aged 45-75 who reside in Petersburg and surrounding counties, and identify as AA/Black and have no personal history of cancer.

Intervention: For Aim 3 and additional criterion is that men have to be due for CRC screening upon study enrollment

Number of Participants

Survey: n=175

Intervention n=30

Study Design

Survey: Cross sectional; qualitative,

Intervention: single arm, pre-post Social behavioral intervention

Study Duration

Survey: 36 months total
 
Intervention: Aim 3: 12 months (once enrolled men are on study for three months)

Outcome Variables
 
Please see survey measures

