
Intervention: Aim 3:
 
Primary Outcome: CRC screening status at 3 months (>60%)
 
Secondary Outcomes:
 
• Intention to screen at 2 weeks (>80%)• Enrollment (target of n=30)• Maintain a retention rate (completion of baseline, 2 and 12 week surveys) >65% at 12 weeks• Viewing videos (# views, # repeat views)• Completion of baseline and follow up questionnaires (retention)• Responding to request to contact clinic/navigation services• Sharing any content with social network

Locations/Facilities
 
Surveys will be completed online
 
Recruitment for surveys will take place in-person, using social media, flyers in public spaces
 
Intervention: Aim 3: Recruitment will take place with flyers, word or mouth and presentations to introduce the study at partner and CAB member places of business and worship. These include community health clinics, local gyms, barbershops, stores, churches. We will use social media, newsletters and text messaging avenues of communication as utilized by our community and clinic partners. We will also use radio announcements on local health focused radio shows.

1 - Background/Literature Review

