4.8 Consent/Assent Procedures

1. We will use an information form that covers all basic elements of consent. We are requesting waiver of all elements of consent for both the survey and the focus group. The survey collects non-identifiable information about attitudes, beliefs and behaviors related to cancer prevention and CRC cancer screening. This will be collected anonymously. The focus groups are small, completed using video conferencing (VCU ZOOM) and will use pseudonyms. The content of the focus groups will be to understand what barbers think the the training needs for becoming a CRC CHamP (i.e., a community resource for information), insights about program marketing and recruitment, how COVID-19 may affect their ability and interest in participating and recruiting. The focus group evaluating the initial QR code intervention will inform the research team on how to tailor the intervention to Black men age 45-75. These are not private information. The consent form would be the only identifying information being collected for the survey participants. The survey responses will be anonymous.
2. The intervention will use a self-administered consent form that participants will complete on their own through the mHealth application (the app).

5 - Study Design

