5.4 Study Procedures

Survey

The survey will be a self-administered electronic survey (e-survey) expected to take 15-20 minutes to complete. Using a secure HIPAA compliant VCU Redcap survey housed on a VCU server, a unique survey link will be provided to interested participants (via email or QR code available on flyers and social media messaging). The secure, unique link will include a screener to determine eligibility, a self-administered information form with consent elements followed by the survey. Participants who complete surveys will receive an electronic gift card of \$20 sent to an email provided by the respondent.

Focus Groups:

Local barbers currently working in a Petersburg or Richmond Barbershop; will be recruited for focus groups. Barbershops are an excellent way to gain intervention 'reach' among our target population, Black men. Barbers within the Petersburg area will be recruited from one of the four community partner barbershops that agree to participate in the study. Barbers will be approached in-person at the shop by a member of the research team) who will visit shops to introduce the study and ask permission to leave study information and/or come back to talk to the group. Focus groups will be conducted virtually using smartphone accessible VCU Zoom and will be video recorded, with permission. Participants will engage in a 60-90-minute discussion.

Aim 3 Intervention:

Men will be invited to participate using all methods outlined above. Men who are interested will be directed to download the app to their personal device. Once the app is downloaded participants are able to self-direct through the screening process. If requested, a study member can assist with downloading the app and navigating through to the study screener.

Potential participants will be asked to complete a screener to ensure all eligibility criteria are met. Those who do not meet eligibility will be thanked for their time and navigated to an exit screen. For those who are eligible, they will next be asked to complete the consent process. After they consent, they will be navigated to the baseline questionnaire. Once completed, they will be able to access all other content (videos, infographics, request link to receive a call from screening navigation, additional surveys for values elicitation).

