5.7 Data Collection

The survey will be a self-administered electronic survey (e-survey) expected to take 15-20 minutes to complete. Using a secure HIPAA compliant VCU Redcap survey housed on a VCU server, a unique survey link will be provided to interested participants (via email or QR code available on flyers and social media messaging).

Focus Groups: Participants (n=16) will be barbers employed at one of the four community partner barbershops. Two virtual focus groups of 6-8 barbers will be conducted. Focus groups will be conducted virtually using smartphone accessible VCU Zoom and will be video recorded, with permission. Participants will receive a \$20 honorarium for the 60-90-minute discussion.

Intervention: Baseline, 2 and 12 week follow up surveys will be collected on the app. If men do not respond to the follow up survey on the app they will be contacted by a study team member and provided alternatives for completion (see study procedures above).

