6.1 Sample Size

The survey component was powered on the interaction term "discrimination*preventive care engagement", both continuous, using a simulation study of 1000 runs of a logistic regression model, with the binary screening behavior response (1 = screened, 0 = not screened). A sample size of 175 subjects generates 80% power to detect a "small to moderate" effect size of 0.38 (corresponding odds ratio = 2.01, using R package "effect size") for the interaction term (continuous*continuous), at 5% level of significance, using a one-sided Z-test. To account for individuals who start but do not complete the survey we have added a buffer of 20% which gives a sample size of n=210 for the survey.

We will also conduct focus groups with n=16 men.

Total project sample size n=226

Intervention Sample Size: To perform an initial test of efficacy, satisfaction and feasibility, we will test the intervention on 30 men.

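### Aim 3 eligibility does not exclude men who already had a role in the project, so some of the 30 may not be newly reached men

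*Combined protocol and SAP*

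**What the plan says.** **Who may enter Aim 3.** Section 4.3 admits adult Black men who "work or live in a Petersburg VA, aged 45-74, eligible for CRC screen at study enrollment". The synopsis takes the survey criteria and adds only that "men have to be due for CRC screening upon study enrollment". Section 5.4 leaves the check to a self-directed app: "Potential participants will be asked to complete a screener to ensure all eligibility criteria are met". No criterion in any of these places concerns a prior role in the project.

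**Who already has a role.** Section 4.2 states: "We require 8-10 men for the Community Advisory Board". Section 5.7 states: "Participants (n=16) will be barbers employed at one of the four community partner barbershops", and then describes two groups of six to eight. Section 4.3 gives board and focus-group men one joint criterion: adult Black men tied by work or home to Petersburg or nearby counties, who need not meet screening requirements themselves.

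**What they do.** Section 4.8 states: "The focus group evaluating the initial QR code intervention will inform the research team on how to tailor the intervention". Section 5.8 has the barber groups advise on how barbers can introduce the intervention and encourage its use. The synopsis names barbers as possible Community Champions, and section 6.2 plans separate interviews with Champions about recruitment.

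**Where Aim 3 recruits.** The synopsis (Locations/Facilities) includes "presentations to introduce the study at partner and CAB member places of business and worship" and lists barbershops among the sites.

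**How Aim 3 is judged.** Section 6.1 says "we will test the intervention on 30 men". The synopsis hypotheses require more than 60% of enrolled men screened by 12 weeks and more than 80% intending to screen at week 2. Section 6.2 adds a benchmark of 80% of consented men viewing materials. Nothing in section 6.2 identifies or separates men by prior role.

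**The concern.** A man who helped tailor the content, or who promotes it to others, has met its messages before his baseline questionnaire. His baseline knowledge, risk perception and intention may already have changed, so his change from baseline does not measure what the app does for a man who meets it for the first time. His viewing, intention and screening results may also reflect his tie to the project.

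The design has little protection against this. There is no comparison arm, the sample is 30, and the results are read against fixed percentages, so a few men can decide whether a benchmark is met.

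Later repair is difficult. Focus groups run under self-chosen names (section 4.5), and section 7.1 says no key will link pseudonyms to the demographic data. Unless prior role is asked at screening, the analysis may be unable to find these men.

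**Working it through.** The plan gives no derivation for the 30 men (no null rate, power or precision), so there is no figure to reproduce. The check covers overlap, pool size and sensitivity of the result.

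**1. Overlap of the criteria**

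| | Board and focus-group men (4.3) | Aim 3 (4.3) | Aim 3 (synopsis) |
|---|---|---|---|
| Age | any adult | 45-74 | 45-75 |
| Tie to area | work or live, Petersburg or nearby counties | work or live, Petersburg | reside, Petersburg and nearby counties |
| Screening status | not required | eligible for screening | due for screening |
| Prior role | – | not mentioned | not mentioned |

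The populations overlap in part. A barber aged 50 who is due for screening and works in the city passes section 4.3. Under the synopsis he must also live in the area.

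**2. Pool.** Board 8-10 (section 4.2). Barbers 2 × 6 = 12 to 2 × 8 = 16 (section 5.7). Lower figure 8 + 12 = 20; upper figure 10 + 16 = 26. Any man in both groups reduces this. The age, due-for-screening and residence filters then apply, and the documents do not say how many men remain. They also give no number of Community Champions beyond these groups.

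**3. Shift in the observed rate.** Let k be the number of such men among the 30, q their screening rate and p the rate in other men; all three are assumptions. The expected shift is k(q − p)/30.

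- Upper bound for one man, replacing a certain non-screener by a certain screener: 1/30 = 3.3 points.
- One man, q = 100%, p = 55%: (1 − 0.55)/30 = 1.5 points.
- Six men, q = 100%, p = 55%: (6 + 24 × 0.55)/30 = 19.2/30 = 64%, against 55% with none.
- Six men, q = 30%, p = 55%: (1.8 + 13.2)/30 = 50%, against 55% with none.

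**4. Chance of meeting the screening benchmark.** Since 0.60 × 30 = 18, exceeding 60% of enrolled men needs at least 19. The exact probability is P(X + Y ≥ 19), with X binomial (30 − k, p) and Y binomial (k, q):

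| p | q | k = 0 | k = 3 | k = 5 |
|---|---|---|---|---|
| 50% | 100% | 10.0% | 22.1% | 34.5% |
| 50% | 80% | 10.0% | 16.7% | 22.6% |
| 55% | 100% | 23.3% | 40.3% | 54.3% |
| 55% | 80% | 23.3% | 32.3% | 39.2% |

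For intention, more than 80% of 30 needs at least 25. With p = 70% and q = 100%, the chance is 7.7% with none, 13.6% with three and 19.3% with five.

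These figures show how sensitive the reading is when q exceeds p. They do not show that q exceeds p here.

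**The case against.** The strongest reply concerns direction. Aim 3 takes only men still due for screening. A man who met the content and acted on it would usually no longer be due. Those who remain may be men who heard the messages and did not act, and they could screen less than newcomers, as in the 50% case above. Higher baseline knowledge would also tend to shrink a pre-post change. This stands: upward bias is a reasonable expectation for men with a stake in the study, but the documents do not establish it.

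The second reply is that the eligible number may be near zero. Board and focus-group men may be any adult age, may already be screened, and may be tied only to nearby counties. Section 5.4 mentions Richmond barbershops too, although section 5.7 names the four partner shops. This also stands, and six such men is purely an illustration.

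The third reply concerns roles. No section says that the advisory board reviews or shapes content; the synopsis only places recruitment at its members' premises. Section 4.8 does not say that the focus group evaluating the QR code intervention is the 16 barbers. A reader might infer that all 20 to 26 men have seen the content, and the text does not support that.

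Finally, section 4.2 presents the 30 men as pilot data on feasibility. That limits the stakes, but the plan still reads effectiveness from the 60% benchmark. None of these replies supplies the missing exclusion.

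**Conclusion.** The omission is real: no Aim 3 criterion, and therefore no screener question required by the plan, keeps out men with a prior role, and recruitment takes place where some of them work or worship. Their results may not represent newly reached men.

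The size is unknown. At most 20 to 26 men are in the named groups before filters. Each enrolled man moves a rate by at most 3.3 points, and by 1.5 in expectation under the stated assumption. Where such men do screen more than others, three to five of them can raise the chance of a positive signal materially.

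A reader might go further and conclude that the uptake result will be inflated, or that most of the 30 places could go to insiders. The documents support neither: they give no count of eligible men and no screening rate for them, and the due-for-screening rule could push the rate either way. This is a cheap improvement to make before enrolment. It does not invalidate the pilot.

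**What to change.** Add to section 4.3, to the synopsis criteria and to the app screener: a man is not eligible for Aim 3 if he served on the advisory board, took part in a focus group, or acts as a Community Champion for this project.

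Optionally add one yes/no baseline item on having already seen the study videos. Use it descriptively or for a secondary sensitivity summary, and keep all eligible enrolled men in the primary result. Men who saw a video should not be dropped: section 4.4 plans to play the study's video in clinic waiting rooms, and section 5.4 invites Aim 3 men by the same methods, so the item will also flag ordinary recruits.

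The cost is one criterion and up to two short questions. The downside is that a few willing men cannot enrol.
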